#### 5.5 Diet/Activity/Other Considerations

#### 5.5.1 Diet

Subjects should maintain a normal diet unless modifications are required to manage an AE such as diarrhea, nausea, or vomiting.

#### 5.5.2 Contraception

Women of childbearing potential are defined as any female who has experienced menarche and who has not undergone surgical sterilization (hysterectomy or bilateral oophorectomy) or who is not postmenopausal. Menopause is defined clinically as 12 months of amenorrhea in a woman over 45 in the absence of other biological or physiological causes. In addition, women under the age of 62 must have a documented serum follicle stimulating hormone (FSH) level greater than 40 mIU/mL to be considered post-menopausal.

Men who are sexually active with WOCBP must use any contraceptive method with a failure rate of less than 1% per year Men receiving study drug and who are sexually active with WOCBP will be instructed to adhere to contraception for a period of 31 weeks after the last dose of investigational product.

Subjects should be informed that taking the study medication may involve unknown risks to the fetus (unborn baby) if pregnancy were to occur during the study. In order to participate in the study they must adhere to the contraception requirements (described above) for the duration of the study and during the follow-up period. If there is any question that a subject will not reliably comply with the requirements for contraception, that subject should not be entered into the study.

#### 5.5.2.1 Highly Effective Methods of Contraception

- Male condoms with spermicide
- Hormonal methods of contraception including combined oral contraceptive pills, vaginal ring, injectables, implants and intrauterine devices (IUDs) such as Mirena® by WOCBP subject or male subject's WOCBP partner Female partners of male subjects participating in the study may use hormone based contraceptives as one of the acceptable methods of contraception since they will not be receiving study drug
- Nonhormonal IUDs, such as ParaGard®
- Tubal ligation
- Vasectomy
- Complete Abstinence\*

\*Complete abstinence is defined as complete avoidance of heterosexual intercourse and is an acceptable form of contraception for all study drugs. Subjects who choose complete abstinence are not required to use a second method of contraception. Acceptable alternate methods of highly effective contraception must be discussed in the event that the subject chooses to forego complete abstinence.

#### 5.5.2.2 Less Effective Methods of Contraception

- Diaphragm with spermicide
- Cervical cap with spermicide
- Vaginal sponge
- Male Condom without spermicide
- Progestin only pills by WOCBP subject or male subject's WOCBP partner
- Female Condom\*.
  - \* A male and female condom must not be used together

#### 5.5.3 Use in Pregnancy

If a subject inadvertently becomes pregnant while on treatment with nivolumab or ipilimumab, the subject will immediately be removed from the study. The site will contact the subject at least monthly and document the subject's status until the pregnancy has been completed or terminated. The outcome of the pregnancy will be reported to the Big Ten Research Consortium (BTCRC) within 24 hours of discovery of event and BTCRC will notify the sponsor-investigator and Bristol-Myers Squibb within 24 hours if the outcome is a serious adverse experience (e.g., death, abortion, congenital anomaly, or other disabling or life-threatening complication to the mother or newborn). The site investigator will make every effort to obtain permission to follow the outcome of the pregnancy and report the condition of the fetus or newborn to BTCRC who will report to Bristol-Myers Squibb. If a male subject impregnates his female partner the study personnel at the site must be informed immediately and the pregnancy reported to the BTCRC who will report to Bristol-Myers Squibb and followed as described above.

#### 6. TOXICITIES AND DOSE DELAYS/DOSE MODIFICATIONS

The NCI Common Terminology Criteria for Adverse Events (CTCAE) v4 will be used to grade adverse events.

Subjects enrolled in this study will be evaluated clinically and with standard laboratory tests before and at regular intervals during their participation in this study as specified in Study Calendar & Evaluations.

Subjects will be evaluated for adverse events (all grades), serious adverse events, and adverse events requiring study drug interruption or discontinuation as specified in Study Calendar & Evaluations.

Subjects discontinued from the treatment phase of the study for any reason will be evaluated 30 days ( $\pm$  7) after the last dose of protocol therapy.

#### 6.1 Dose Delays/Dose Modifications

Nivolumab and/or ipilimumab will be withheld for drug-related: Grade 4 hematologic toxicities, nonhematological toxicity  $\geq$  Grade 3 including laboratory abnormalities, and severe or life-threatening AEs as per the table below. Protocol therapy will also be held for some persistent grade 2 toxicities (please see table below).

There are no dose reductions for either nivolumab or ipilimumab. For toxicity as outlined in this protocol, study therapy should be delayed until the adverse event improves to the stated level or should be discontinued permanently depending on severity (see table below and section 5.4).

Toxicity Hold Treatment For		Timing for Restarting Treatment	Discontinue Subject
Diarrhea/Colitis	Grade 2-3	Toxicity resolves to Grade 0-1	Toxicity does not resolve within 6 weeks of last dose unless delay beyond 6 weeks allows for prolonged steroid taper to manage toxicity. In such cases, the Sponsor Investigator must be consulted prior to re-initiating treatment.
	Grade 4	Permanently discontinue	Permanently discontinue
Pneumonitis	Grade 2	Toxicity resolves to Grade 0-1	Toxicity does not resolve within 6 weeks of last dose unless delay beyond 6 weeks allows for prolonged steroid taper to manage toxicity. In such cases, the Sponsor Investigator must be consulted prior to re-initiating treatment.
	Grade 3-4	Permanently discontinue	Permanently discontinue
Hepatitis	$\geq$ Grade 2 if subject has baseline AST, ALT or total bilirubin that is within	Toxicity resolves to Grade 0-1	Toxicity does not resolve within 6 weeks of last dose unless delay beyond 6 weeks

Encephalitis	New-onset moderate or severe neurologic signs or symptoms	Toxicity resolves to Grade 0-1	Toxicity does not resolve within 6 weeks of last dose unless delay beyond 6 weeks allows for prolonged steroid taper to manage toxicity. In such cases, the Sponsor Investigator must be consulted prior to re-initiating treatment.		
	Immune-mediated encephalitis	Permanently discontinue	Permanently discontinue		
Adrenal Insufficiency	Grade 2	Toxicity resolves to Grade 0-1 even if requires physiologic hormone replacement	Toxicity does not resolve within 12 weeks of last dose.		
	Grade 3-4	May need to permanently discontinue; see footnote #4	May need to permanently discontinue; see footnote #4		
Uveitis 	≥Grade 2	Permanently discontinue	Permanently discontinue		
Thrombocytopenia	Grade 3 >7 days or associated with bleeding or Grade 4	Permanently discontinue	Permanently discontinue		
All Other Drug	Grade 2 	Toxicity resolves to Grade 0-1 even if requires physiologic hormone replacement for drug related endocrinopathy	Toxicity does not resolve within 6 weeks of last dose unless delay beyond 6 weeks allows for prolonged steroid taper to manage toxicity. In such cases, the Sponsor Investigator must be consulted prior to re-initiating treatment Toxicity does not resolve within 6 weeks of last dose unless delay beyond 6 weeks allows for prolonged steroid taper to manage toxicity. In such cases, the Sponsor Investigator must be consulted prior to re-initiating treatment		
All Other Drug- Related Toxicity	Grade 3 or severe 	Toxicity resolves to Grade 0-1 even if requires physiologic hormone replacement for drug related endocrinopathy			
	Grade 4 	Permanently discontinue	Permanently discontinue		

 Uveitis or blurred vision that does not respond to topical therapy and does not improve to Grade 1 severity within the re-treatment period OR requires systemic treatment

 Exceptions include grade 2 drug-related fatigue or laboratory abnormalities; do not delay for these events.

 Exceptions include grade 3 lymphopenia or leukopenia; do not delay for these events. In addition, any Grade  $\geq$  3 drug-related amylase or lipase abnormality that is not associated with symptoms or clinical manifestations of pancreatitis does not require dose delay. The Investigator should be consulted for such Grade  $\geq$  3 amylase or lipase abnormalities.

In case toxicity does not resolve to Grade 0-1 within 12 weeks after last infusion, trial treatment should be discontinued after consultation with BTCRC and the sponsor-investigator. With site investigator and sponsor-investigator agreement, subjects with a laboratory adverse event still at Grade 2 after 12 weeks may continue treatment in the trial only if asymptomatic and controlled. For information on the management of adverse events, see Section 5.3. If a subject has a delay of more than 12 weeks or more than 3 delays in study drug dosing due to toxicities they will be discontinued from the trial treatment.

Subjects who experience a recurrence of the same severe or life-threatening event at the same grade or greater with re-challenge of nivolumab or ipilimumab should be discontinued from trial treatment.

For subjects on Arm 2 with immune-related adverse events, the assessment for discontinuation of ipilimumab should be made separately from the assessment for discontinuation of nivolumab. Although there is overlap among the discontinuation criteria, if criteria are met for ipilimumab but not for nivolumab, treatment with nivolumab may continue if ipilimumab is discontinued. If a subject meets criteria for discontinuation and treating physician is unable to determine whether the event is related to nivolumab or ipilimumab, the subject should discontinue both nivolumab and ipilimumab.

#### 6.2 Subject Withdrawal/Discontinuation Criteria

Subjects may withdraw consent at any time for any reason or be withdrawn from the trial at the discretion of the site investigator should any untoward effect occur. In addition, a subject may be withdrawn by the sponsor-investigator or BTCRC if enrollment into the trial is inappropriate, the trial plan is violated, or for administrative and/or other safety reasons. Specific details regarding discontinuation or withdrawal are provided below.

A subject must be discontinued from the trial treatment for any of the following reasons:

- Confirmed radiographic disease progression by RECIST 1.1 criteria
- Unacceptable adverse experiences as described in Section 5.3 and 11.1

- Intercurrent illness that prevents further administration of treatment
- Site investigator's decision to withdraw the subject
- A female subject has a confirmed positive serum/urine pregnancy test
- Noncompliance with trial treatment or procedure requirements
- Completed 6 months of treatment with protocol therapy
- Subject refuses further treatment
- If a subject has a treatment delay of more than 12 weeks from last infusion. See section 6.1.

A subject must be discontinued from the trial for any of the following reasons:

- Administrative reasons
- The subject or legal representative (such as a parent or legal guardian) withdraws consent.
- The subject is lost to follow-up

The End of Treatment and Follow-up visit procedures are listed in Section 7 (Study Schedule of Events and Visit Requirements). After the end of treatment, each subject will be followed for 100 days for adverse event monitoring (serious adverse events will be collected for 100 days after the end of treatment as described in Section 12.2.2). Subjects who discontinue for reasons other than progressive disease will have post-treatment follow-up for disease status until disease progression, initiating a non-study cancer treatment, withdrawing consent or becoming lost to follow-up. After documented disease progression each subject will be followed for survival for up to 2 years, withdrawal of consent, or the end of the study, whichever occurs first.

When a subject discontinues/withdraws prior to trial completion, all applicable activities scheduled for the final trial visit should be performed at the time of discontinuation. Any adverse events which are present at the time of discontinuation/withdrawal should be followed in accordance with the safety requirements outlined in Section 12.2.1 – AE Reporting).

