#### **Arm 1- Key to Footnotes**

- 1. Medical history to include demographics, trial awareness question, smoking history, prior treatments, radiation and surgical history. Smoking history to include: amount, frequency, start and stop dates of cigarette, cigar and pipe usage. If subject has prior genetic sequencing analyses results available, those results should be submitted by end of Cycle 1.
- 2. Treatment-related adverse events will be followed until resolution, return to baseline, or deemed clinically insignificant. Adverse events (from time of consent) and concomitant medications (28 days prior to start of protocol treatment) should be assessed and recorded until 100 days after last dose of study drug. SAE's and the conmeds used to treat them will be collected up to 100 days post treatment.
- 3. Collection of radiation treatment plan data can take place any time during the study. Data such as total lung volume, V20, and additional radiation parameters will be collected. See Documents/Info tab of the EDC. This data will be recorded in the database for future analysis, but it will not affect treatment while on study and is not required to be collected prior to enrollment or initiation of treatment.
- 4. C1D1 testing does not need to be repeated if performed within 7 days of starting protocol therapy.
- 5. Measured or calculated creatinine clearance (GFR can also be used in place of creatinine or CrCl). Erythrocyte Sedimentation Rate (ESR); C-Reactive Protein (CRP); von Willebrand Factor antigen (vWF Ag). Collect ESR, CRP, vWF and ferritin pre-treatment on C1D1, C2D1 and either at the End of Treatment or if the subject develops any grade 3-4 pneumonitis.
- 6. Thyroid function testing: Perform TSH, T3, T4 at baseline and at odd cycles starting at cycle 3 (i.e. Q 8 wks). T3, T4: free/ total as per local standards.
- 7. For women of childbearing potential. Must have negative pregnancy test within 7 days of registration. Women < 62 yrs old must have FSH > 40 mIU/mL to be considered post-menopausal.
- 8. A pathology report confirming the diagnosis of NSCLC must be obtained and reviewed by the treating physician prior to registration to study.
- 9. All patients require Chest CT through adrenals or PET-CT at the time of screening and at subsequent imaging time points. Abdomen or pelvic CTs or bone scans can be included at the discretion of the treating physician should it be clinically indicated, but these are not mandatory.

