- 10. Screening scan including at least CT portion of the chest and abdomen must be performed within 56 days after the completion of chemoradiation or consolidation. PET CT may be done in place of regular CT scans at the discretion of the site investigator. Baseline scans should be done within 28 days prior to treatment initiation. Radiographic disease assessment will be done every 12 weeks ± 4 weeks during study treatment. The scan interval may be reset if scans were done early for clinical reasons. See also 8.3.
- 11. After completion of protocol therapy, subjects who discontinue for reasons other than progressive disease will have post-treatment follow-up for disease status until disease progression, initiating a non-study cancer treatment, withdrawing consent or becoming lost to follow-up. Post treatment radiographic disease assessment should be performed every 3 months until progression. After documented disease progression each subject will be followed for survival every 3 months for up to 2 years, withdrawal of consent, or the end of the study (whichever occurs first).
- 12. A head MRI or CT should be done prior to study treatment for subjects that are symptomatic or have not had prior brain imaging.
- 13. For subjects who meet all eligibility criteria and have recovered sufficiently from treatment with chemoradiation, initial consolidation therapy with nivolumab will be started within 56 days after chemoradiation is complete. For subjects who meet all eligibility criteria after completion of up to two consolidation chemotherapy treatments, therapy with nivolumab will be started within 56 days after last cycle of chemotherapy.
- 14. Mandatory submission of unstained slides from an archived tumor block (if available) for PD-L1, CD4, CD8 by IHC. In addition, whole exome sequencing, RNA sequencing, methylation analysis will be performed. See Correlative Laboratory Manual (CLM) for collection, labeling and shipping instructions.
- 15. Mandatory blood samples for correlative testing should be drawn pre-treatment on C1D1, C2D1 and either at the End of Treatment Visit or if the subject develops any grade 3-4 pneumonitis. See CLM for collection, labeling, and shipping instructions.
- 16. If subject has a bronchoscopy with BAL for clinical reasons, please collect a portion of the of BAL fluid for correlative analysis (optional).

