## 8.4 Safety Follow-up Evaluations

A safety follow-up visit should occur when subjects permanently stop study treatment for whatever reason (toxicity, progression, or at discretion of site investigator) and should be performed 30 days ( $\pm$ 7 days) after the last dose of treatment. Subjects who have an ongoing  $\geq$  grade 2 or serious AE (SAE) at this visit will continue to be followed until the AE resolves to  $\leq$  Grade 1 or baseline, is deemed clinically insignificant, and/or until a new anti-cancer treatment starts, whichever is earlier.

- Physical examination including vital signs (blood pressure, weight)
- ECOG performance status
- Complete Metabolic Profile
- Complete Blood Count with differential
- ESR, CRP, vWF Ag and ferritin
- Adverse events, and concomitant medications must be assessed. Treatment-related adverse events will be followed until resolution, return to baseline, or deemed clinically insignificant. Adverse events (from time of consent) and concomitant medications (28 days prior to start of protocol treatment) should be assessed and recorded until 100 days after last dose of study drug. SAE's and the conmeds used to treat them will be collected up to 100 days post treatment. See Section 8.5 below.
- Mandatory blood samples for correlative testing and optional samples for banking will be drawn

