## 8.5 Long Term Follow-up Evaluations

After completion of protocol therapy, subjects who discontinue for reasons other than progressive disease will have post-treatment follow-up for disease status until disease progression, initiating a non-study cancer treatment, withdrawing consent or becoming lost to follow-up. After documented disease progression each subject will be followed for survival every 3 months ( $\pm$  4 weeks) for up to 2 years, withdrawal of consent, or the end of the study (whichever occurs first).

• Treatment-related adverse events will be followed until resolution, return to baseline, or deemed clinically insignificant. Adverse events (from time of consent) and concomitant medications (28 days prior to start of protocol treatment) should be assessed and recorded until 100 days after last

dose of study drug or until a new anti-cancer treatment starts, whichever is earlier. SAE's and the conmeds used to treat them will be collected up to 100 days post treatment.

• For subjects who discontinue for reasons other than progressive disease, radiographic disease assessment should be performed every 3 months for up to 2 years until progression, initiating a non-study cancer treatment, withdrawing consent or becoming lost to follow-up. The scan interval may be reset if scans were done sooner for clinical reasons. PET CT may be done in place of regular CT scans at the discretion of the site investigator. This imaging may be done locally. Once patients are off treatment and on follow-up, the window for imaging is ±4 weeks.

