## 12.2 Reporting

## 12.2.1 Adverse Events

- AEs will be recorded from time of signed informed consent until 100 days after discontinuation of study drug(s) or until a new anti-cancer treatment starts, whichever is earlier.
- AEs will be recorded regardless of whether or not they are considered related to the study drug(s).
- All AEs will be recorded in the subject's medical record and on the appropriate study specific eCRF form within OnCore.
- All AEs considered related to study drug(s) will be followed until resolution to ≤ Grade 1 or baseline, deemed clinically insignificant, and/or until a new anti-cancer treatment starts, whichever occurs first.
- Asymptomatic laboratory abnormalities that do not require treatment will not be collected as adverse events.

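### A subject who starts non-study cancer therapy before documented progression leaves scheduled disease follow-up and never enters scheduled survival follow-up, so deaths and metastases can be missed

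*Combined protocol and SAP*

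**What the plan says.** **Disease follow-up.** Section 6.2 gives subjects who stop treatment for a reason other than progression "post-treatment follow-up for disease status until disease progression, initiating a non-study cancer treatment, withdrawing consent or becoming lost to follow-up". Section 8.5 and footnote 11 of both calendars use the same list of end points. On imaging, 8.5 adds "radiographic disease assessment should be performed every 3 months for up to 2 years until progression", and again lists the start of non-study therapy among the reasons to stop.

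**Survival follow-up.** Footnote 11 of the Arm 1 calendar reads "After documented disease progression each subject will be followed for survival every 3 months for up to 2 years". The Arm 2 footnote has the same words, and 6.2 and 8.5 use the same trigger. The calendar row for progression and survival refers back to footnote 11, so it adds no contact of its own.

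**Other contacts.** Section 8.4 says "A safety follow-up visit should occur when subjects permanently stop study treatment for whatever reason", timed 30 days (±7) after the last dose. For early discontinuation, 6.2 says "all applicable activities scheduled for the final trial visit should be performed at the time of discontinuation". On adverse events (AEs) and serious adverse events (SAEs), 6.2 says "serious adverse events will be collected for 100 days after the end of treatment as described in Section 12.2.2". Footnote 2 of both calendars and section 8.5 say "SAE's and the conmeds used to treat them will be collected up to 100 days post treatment". Sections 12.2.1 and 12.2.2.1 collect "until 100 days after discontinuation of study drug(s) or until a new anti-cancer treatment starts, whichever is earlier".

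**Endpoints.** PFS counts RECIST 1.1 progression or any death (2.2.1, 13.2.1), and OS counts any death (2.2.2, 13.2.2). Both are analysed in the randomized population (13.7.1, 13.7.2). Section 10.8.6 censors PFS at the last disease evaluation for subjects without progression.

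**The concern.** The two follow-up tracks do not meet. Starting other therapy closes the disease track, and only documented progression opens the survival track. A subject can therefore leave the first without any scheduled assessment that would admit them to the second.

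The route is plausible. Treatment lasts at most 24 weeks (5.1), and section 5.3.2 prohibits no therapy afterwards. Section 10.7 also foresees patients who stop for clinical decline without objective progression.

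Deaths not collected prospectively may be hard to recover later. OS needs every death. Time to metastatic disease, which treats death from other causes as a competing risk (13.7.2), needs deaths and metastases. PFS needs deaths as well as progressions. If those who leave have a worse outlook, censoring them would also raise the estimated 18-month PFS rate, which is tested against fixed rates of 30% and 44%.

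**Working it through.** **1. The gap, state by state** (6.2, 8.5, footnote 11)

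| State after treatment | Scheduled disease follow-up | Scheduled survival contact |
|---|---|---|
| No progression, no other therapy | 3-monthly imaging | Through the imaging visits |
| Documented progression | Ended | 3-monthly, up to 2 years |
| Other therapy, no documented progression | Ended | None |

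**2. What the safety window covers**

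Take treatment on schedule, with day counts from the first dose.
- Arm 1, six 28-day cycles (5.2.3.1): last dose at 5 × 28 = 140 days; 140 + 100 = 240 days; 240 / 30.44 = 7.9 months.
- Arm 2, four 42-day cycles with a last nivolumab dose on day 29 (5.2.4.1): 3 × 42 + 28 = 154 days; 154 + 100 = 254 days; 254 / 30.44 = 8.3 months.

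On the widest reading the window closes 18 − 7.9 = 10.1 or 18 − 8.3 = 9.7 months before the endpoint. It closes earlier if treatment stops early, and under 12.2.1 and 12.2.2.1 it closes at new therapy. Inside the window, 12.1.1 and 12.1.2 keep progression, and death from progression, out of AE and SAE reporting unless attributed to study treatment. The window therefore gives little cover for these endpoints.

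**3. The plan's own figures**

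Section 13.3 states 51 and 48 evaluable subjects for one-sided 0.10 and 80% power. On the log cumulative-hazard scale, n = [(1.2816 √g(p0) + 0.8416 √g(p1)) / D]², with g(p) = (1 − p) / (p ln² p) and D = |ln(−ln p0) − ln(−ln p1)|.
- Arm 1 (0.30 v 0.44): 52.8, so 53.
- Arm 2 (0.44 v 0.59): 48.9, so 49.

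Both are within 2 of the plan. The 5% allowance gives 51 / 0.95 = 53.7, so 54, and 48 / 0.95 = 50.5, so 51, as stated. The sample size is not in dispute.

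**4. Possible effect on the PFS test (assumed scenarios)**

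The documents give neither a leaver rate nor leavers' risk. Set-up: 200,000 simulated arms per cell, n = 54 and 51, exponential PFS, uniform accrual over 24 months, cutoff at 48 months. A share of 5% or 10% is designated to leave at a uniform time in months 0 to 12, with the hazard multiplied by HR afterwards. The baseline hazard is set so that true 18-month PFS equals 30% or 44%. Leavers still event-free are censored at the preceding 3-monthly scan, as 10.8.6 implies. The test rejects if (S − p0) / SE > 1.2816, using the Kaplan-Meier estimate and Greenwood SE as a stand-in for the sign test in 13.7.1.

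Type I error, nominal 0.10:

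| | HR 1 | HR 1.5 | HR 2 |
|---|---|---|---|
| Arm 1, 5% leave | 0.087 | 0.100 | 0.109 |
| Arm 1, 10% leave | 0.083 | 0.108 | 0.130 |
| Arm 2, 5% leave | 0.095 | 0.108 | 0.119 |
| Arm 2, 10% leave | 0.094 | 0.120 | 0.143 |

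At 10%, about 4 subjects per arm actually leave event-free; at 5%, about 2. The mean Kaplan-Meier estimate at 10% is 29.7 / 30.7 / 31.4% in Arm 1 and 43.7 / 44.7 / 45.5% in Arm 2, so the largest shift is 45.5 − 44 = 1.5 points. With complete follow-up, type I error is about 0.10 in Arm 1 and 0.08 in Arm 2; the latter reflects the discreteness of the test.

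**5. Test scale**

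For Arm 2 at 10% and HR 2, one run gave 0.144 with the untransformed test and 0.131 on the log cumulative-hazard scale.

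**The case against.** The strongest reply is that the PFS effect is conjectural and probably minor. It stands in large part. In Arm 1 with 5% leaving and HR 2, type I error is 0.109, less than 0.01 above complete follow-up. With no raised risk the test does not exceed its nominal level. The Arm 2 figure moves with the test scale.

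It is also fair that PFS handling is not a void. Section 10.8.6 supplies a default censoring rule, so a sentence in 13.7.1 would clarify rather than repair. A site may also record progression found in usual care and then begin survival contact. Section 10.7 asks sites to try to document progression after treatment, and the safety board reviews deaths on study (14.2). None of these sets a contact.

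Three stronger readings are tempting but unsupported:
- A reader might infer that the protocol ends survival follow-up at new therapy. No section says so; the gap is an omission.
- A reader might infer a badly inflated primary test. If 10% of subjects with an event by month 18 start other therapy first and are censored at the preceding scan, type I error is 0.21 (Arm 1) and 0.19 (Arm 2). That makes every leaver someone about to have an event, which nothing in the documents supports.
- A reader might cite the share of all 18-month events that fall after the safety window. That share describes every subject, and those who have not started other therapy remain under 3-monthly imaging until progression.

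**Conclusion.** The gap is certain from the text and appears in every section that governs follow-up. Its firm consequence needs no assumption about risk: for subjects who start other therapy before documented progression, deaths and metastases are incompletely ascertained for OS and time to metastatic disease, and deaths for PFS.

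The effect on the primary test is uncertain in size. An upward bias in 18-month PFS requires that these subjects be at raised risk. Under the assumed scenarios it is small at 5% leaving. At 10% and HR 2, type I error is about 0.13 in Arm 1 and 0.13 to 0.14 in Arm 2. Whether the 30% and 44% reference rates carry a similar bias cannot be judged, because the cited trial's handling of new therapy is not in the documents. The point is worth fixing because the repair is cheap, not because the primary result is shown to be unsound.

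**What to change.** In 6.2, 8.5 and footnote 11 of both calendars, state that the existing 3-monthly survival contact applies to every living randomized subject after treatment, whether or not they have progressed or started non-study therapy, unless consent to follow-up is withdrawn. Record progression or metastasis seen on usual-care scans.

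As a minor addition, say in 13.7.1 that the 10.8.6 censoring rule is the default when non-study therapy starts before progression. A supportive analysis counting that start as an event is optional. It departs from the endpoint definition and is conservative: power is 0.59 to 0.76 in Arm 1 and 0.45 to 0.66 in Arm 2, against 0.81 and 0.77 with complete follow-up.

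Separately, reconcile the SAE window in 8.5, which has no cut-off at new therapy for SAEs, with 12.2.2.1, which has one.

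The cost is a short amendment and a few extra contacts. No scan is mandated, and treatment, sample size and primary test are unchanged. Progression after new therapy will still be only partly captured. If the later course of half the leavers is fully observed, type I error at 10% and HR 2 falls from 0.130 to 0.109 (Arm 1) and from 0.143 to 0.117 (Arm 2).
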